6.2 High Risk Cohort Sample Size for Primary Outcomes

The second population of interest comprises the cohort of high-risk population of women delivering in facilities with high risk being defined as term and preterm pregnant women who experience prolonged labor or prolonged membrane rupture. As a major secondary aim, sample size estimates for the high-risk cohort were also obtained to ensure adequate power for this analysis.

The primary objective of the high-risk component of the study is to test the effectiveness of a single oral dose of intrapartum azithromycin prophylaxis compared to placebo (all receive usual care) in reducing the risk of maternal sepsis or death in high risk laboring women. To estimate the sample size required for this component of the study, we assumed conservatively that the underlying risk of the combined outcome in the target population is 6%. Comparable to the other study estimates of the required sample size needed to detect a risk reduction of 20%, 25%, and 30% were generated for power of 0.8, 0.85, and 0.9. Because the interest for this study is in testing the hypothesis overall rather than by region, the estimates were generated using an alpha of 0.05. The results of these calculations are shown in Table 3 below.

Table 3. Sample Sizes for the High-Risk Cohort, Alpha=0.05

Baseline risk	Risk Reduction	Evaluable Sample Size per Arm		
		Power=0.80	Power=0.85	Power=0.90
6%	20%	5568	6369	7453
6%	25%	3470	3969	4644
6%	30%	2344	2681	3138

Because a risk reduction of at least 30% is expected in this population, we propose a sample size for this HR cohort of 5,500 women. That sample size will be sufficient to detect a 30% risk reduction with a power of 0.85 with an assumed 2% to 3% loss to follow-up. Assuming that 20% of the women are at high risk, the overall study sample size of 34,000 should allow for sufficient enrollment into the HR cohort.

7. STATISTICAL / ANALYTICAL ISSUES

7.1 General Rules

All statistical computations will be performed and data summaries will be created using SAS 9.3 or higher. If additional statistical packages are required, these will be discussed in the study report. For summaries of study data, categorical measures will be summarized in tables listing the frequency and the percentage of participants in each study arm; continuous data will be summarized by presenting mean, standard deviation, median, minimum, and maximum; and ordinal data will be summarized by presenting median and the limits of the interquartile range.

7.2 Adjustments for Covariates

As this is a randomized trial and the randomization process was not compromised during execution, the treatment effect estimate from trial is unbiased, even without adjusting for any baseline covariates. Therefore, no adjustments for covariates other than site as a randomization stratification factor are planned for the primary analysis. However, baseline clinical and demographic variables that are known predictors of neonatal and maternal outcomes will be included in secondary analyses of intervention efficacy.

7.3 Missing Data Approaches:

The two primary reasons for missing data are expected to be 1) participant loss to follow-up and 2) lack of record availability of unscheduled clinic visit, hospitalizations and readmissions required to diagnose infections.

Based on the historical data available from the M NH registry, we anticipate that the rate of missing responses due to loss to follow-up for maternal and neonatal morbidity and mortality measures are likely to be 2% or less. This rate has been confirmed based on the pilot data where the current rate is 1.1% for participants loss to follow-up or who were withdrawn or withdrew themselves from study participation.

All suspected infections that cannot be programmatically confirmed will go through a local site and central adjudication process to determine final outcome status using all available information as described in the adjudication plan. We anticipate the rate of cases that cannot be adjudicated to be low; estimates of that proportion will be obtained using pilot data prior to any unmasking or analyses of the main trial data.

For the primary analyses of sepsis and/or death in the ITT population, missing responses due to loss to follow-up and cases of suspected infection that cannot be adjudicated will be included via multiple imputation procedures. Multiple imputation assumes that the mechanism that caused the missing is independent of the value of the unobserved data (i.e. data are missing at random – MAR). Although there is potential that missing data due to record availability may not be MAR, we anticipate this proportion of missing data will be small and multiple imputation processes have been shown to be robust even if the missing mechanism is dependent on the values of the unobserved data, i.e. even if the missing data are non-ignorable non-response. As secondary/sensitivity

analyses, the primary analyses will also be repeated on the ITT populations using data as available and assuming all missing outcomes are sepsis or death as well as assuming all missing outcomes are not sepsis nor death.

If more than 4% of data in within either or across both arms are missing for any reason, we will conduct additional sensitivity analysis on the effect of missing data on the inference including analyzing data as available and other approaches that will assess the robustness of the findings to different assumptions about the missing data. The exact approaches for these sensitivity analyses will be determined based on the pattern of missingness and detailed in the final study report.

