4.1 Data Forms

The following forms will be used for this study:

Form Name	Purpose	Key Data Elements	Data Source
Contact and Scheduling Form	To facilitate participant follow-up by documenting contact information and projected study visit schedule	Contact information, date of enrollment, date of follow-up visits	Participant interview, study calendar
Screening and Enrollment Form	To determine eligibility and record consent status	Screening date, review and confirmation of inclusion/exclusion criteria, consent status/date.	Participant interview/report, clinical assessment, provider report, medical records
Randomization Form	To confirm eligibility and track randomization	Eligibility confirmation, randomization date/time, drug administration date/time, any problems with drug administration (e.g., vomiting, dropped med, etc).	Study records, participant interview and observation

Form Name	Purpose	Key Data Elements	Data Source
Maternal Baseline Data Form	To collect additional maternal information	
 Demographic and baseline clinical data: admission date/time, EDD, GA, age, height, weight, pregnancy and medical history, etc. Events during labor and delivery: timing of onset of labor, prolonged labor, premature rupture of membranes, date/time/type of membrane rupture, date/time/type of delivery, indication for induction (if applicable), vital signs during labor (temp, HR, RR, BP), complications, etc. Events after delivery: complications, vital signs, etc. Infection assessment pre- and post-delivery Antibiotic treatment pre- and post-delivery Discharge information 	Participant interview/report, provider report, medical records
Neonatal Baseline Data Form	To collect information about the infant directly after delivery.	
 Sex Birthweight Delivery outcome (live or stillbirth) Complications Infection assessment Discharge information: date/time, status (discharged, transferred, died) 	Participant interview/report, provider report, medical records
Maternal and Neonatal Follow-up Form	To collect maternal and infant health status during follow-up visits at 3 days, 7 days and 42 days after delivery.	
 Timing follow-up Maternal and infant status since discharge: general status, symptoms, indication of infection, clinic visits, hospitalizations, antibiotic use Temperature 	In-person participant interview/report and clinical exam

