- **The Maternal Newborn Health Registry** is a prospective, population-based study of pregnancies and their outcomes in low-middle income countries (DRC, Guatemala, India, Pakistan, Bangladesh, Zambia and Kenya). All pregnant women in participating clusters are registered and their outcomes tracked for 6 weeks post-delivery. The primary purpose of this prospective, population-based observational study of approximately 60,000 women per year is to quantify and understand the trends in pregnancy services and outcomes over time in defined, low-resource geographic clusters. The goal is to provide population-based statistics on stillbirths, neonatal and maternal mortality as the basis of health care policy. The data from the registry also provide the mortality and morbidity outcomes for Global Network trials and help investigators plan future studies for the Global Network.
- Preterm birth remains the leading cause of neonatal mortality and long-term disability throughout the developed and developing world. A growing body of evidence suggests that 1st

trimester administration of low dose aspirin can reduce the rate of PTB substantially. The **ASPIRIN Study** is a prospective, randomized, placebo-controlled, double-masked, multi-center clinical trial to examine whether low dose aspirin initiated between 6 0/7 weeks- 12 6/7 weeks gestation reduces the risk of preterm birth. The study has enrolled 11,920 women across seven sites in Africa, Asia, and Latin America.

- Attention is increasingly directed to the role of maternal nutrition during the 1st trimester for normal growth and development during the first thousand days, from conception to the child's second birthday. The primary hypothesis of the **Women First: Preconception Maternal Nutrition study** is that for women in poor communities, a comprehensive maternal nutrition intervention commencing at least 3 months prior to conception and continuing throughout pregnancy, will be associated with a significantly greater newborn length than for offspring whose mothers start to receive the same intervention at 12 weeks gestation or who do not receive the intervention at all. The results of this trial will make a major contribution to refining evidence-based strategies for maternal nutrition supplementation and evaluating the cost-benefits of extending such strategies beyond pregnancy to virtually all women of child-bearing age, including adolescent girls.

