9.3 Primary Analysis

The primary outcomes of incidence of maternal death or sepsis and incidence of intrapartum/neonatal death or sepsis will be compared between the two treatment arms using generalized linear models. These generalized linear models will be fit with each binary outcome separately as the outcome measure. Estimates of relative risk and associated 95% confidence intervals will be reported. The model will include terms for treatment and site. As randomization occurs at the pregnancy level and approximately 1-2% of pregnancies are anticipated to be multiple gestations, models for neonatal outcomes will account for correlation among multiples assuming an exchangeable covariance structure. If a model for neonatal outcomes has convergence issues, then the generalized linear model will be fit without the adjustment for correlation among multiples. For the two primary outcomes, these analyses will be conducted using the ITT population and the p-values associated with the treatment term will be used to formally test each of the two primary hypotheses at the alpha = 0.05 level.

The primary analyses using the ITT population will use multiple imputation for missing outcomes implemented separately for mothers vs. infants via logistic regression imputation using site and high-risk status prior to randomization as covariates. As sensitivity analyses, the primary outcomes will also be analyzed without imputation for individuals in the ITT population, without imputation for individuals in the per-protocol population; and in the ITT population assuming all missing outcomes are sepsis or death as well as assuming all missing outcomes are not sepsis nor death.

As secondary analyses of the primary outcomes, the models will be run including region (Africa, Latin America, or Asia) and a treatment by region interaction term. If the interaction term has a $p<0.1$, then effect estimates and associated confidence intervals will be reported by region with treatment effect within region for Africa and Asia tested at the 0.025 level.

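### The site-only primary models are valid, but they forgo a small precision gain from high-risk status and gestational age, and no planned analysis is certain to use either as a named adjustment covariate

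*Combined protocol and SAP*

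**What the plan says.** SAP 9.3 specifies the primary models in one line: "The model will include terms for treatment and site". Protocol 3.1.1 gives the same terms, with exchangeable correlation for multiples in the neonatal models. SAP 7.2 gives the reason (no bias under randomization) and the rule: "no adjustments for covariates other than site as a randomization stratification factor are planned for the primary analysis".

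Other baseline predictors are deferred. SAP 7.2 says that "baseline clinical and demographic variables that are known predictors of neonatal and maternal outcomes will be included in secondary analyses of intervention efficacy", without naming any. The exploratory models in SAP 9.3 add variables found to differ significantly between the arms. The baseline variables listed in SAP 8.4 (maternal age, education, marital status, parity, infection during pregnancy, outcome of last pregnancy) include neither gestational age nor high-risk status.

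Both predictors are collected. The Maternal Baseline Data Form (protocol 4.1) records "admission date/time, EDD, GA, age, height, weight, pregnancy and medical history" and "timing of onset of labor, prolonged labor, premature rupture of membranes, date/time/type of membrane rupture". Gestational age of at least 28 weeks by best estimate is also an eligibility criterion (protocol 2.2.1), so it is assessed before randomization. High-risk status is already used to impute missing primary outcomes, by "logistic regression imputation using site and high-risk status prior to randomization as covariates".

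**The concern.** Lack of bias is a reason why adjustment is not needed for validity. It says nothing about the width of the confidence interval. A pre-specified term for a baseline predictor leaves the type I error intact. Under a common relative risk it also leaves the estimand unchanged, because the relative risk is collapsible. What is at stake is precision obtained without recruiting anyone.

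The documents themselves treat both variables as prognostic. The assumed maternal risk is 6% in high-risk women (SAP 6.2) against 3% overall (SAP 6.1). For gestational age the support is qualitative: "Preterm birth remains the leading cause of neonatal mortality and long-term disability throughout the developed and developing world" (protocol Appendix 1, in the description of another trial).

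The deferred adjustment does not clearly fill the gap. Unnamed predictors leave the choice open, and selecting covariates by significant difference between arms selects on chance imbalance rather than on prognosis.

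**Working it through.** **The plan's own figure.** Inputs from SAP 6.1: 3.0% against 2.4% (20% reduction), two-sided alpha 0.05, power 90%. With the pooled two-proportion formula:

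n = [1.96·√(2·0.027·0.973) + 1.2816·√(0.03·0.97 + 0.024·0.976)]² / 0.006² = (0.4493 + 0.2937)² / 0.000036 ≈ 15,334 per arm, which matches SAP Table 1.

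**Power as planned.** 34,000 women less 3% loss leaves 17,000 × 0.97 = 16,490 per arm. Power = Φ[(0.006·√16,490 − 0.4493)/0.2292] = Φ(1.40) = 91.95%. At 2% loss it is 92.2%. Using the final-analysis alpha of 0.0499 gives 91.94% at 3% loss.

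**Effect of a covariate.** For a log-link model with a common relative risk of 0.8, the variance of the log relative risk per woman per arm at control risk p is

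v(p) = (1−p)/p + (1−0.8p)/(0.8p) = 2.25/p − 2.

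Unadjusted, v(0.03) = 73. Adjusted for strata with shares s and control risks p_s, the variance is 1/Σ[s/v(p_s)].

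**Maternal outcome, high-risk status.** The share is 10-20% (protocol 1.6.3), with 20% used in SAP 6.2. The risk in high-risk women is 6%, and the rest is set so that the overall risk stays at 3%. The second pair of rows uses protocol 1.4.2, where lower-risk women may account for about half of infections, so high-risk women carry the other half.

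| Share | Risk, high-risk / other | v, high-risk / other | Adjusted variance | Variance cut | SE cut | Power |
|---|---|---|---|---|---|---|
| 10% | 6% / 2.67% | 35.5 / 82.4 | 72.77 | 0.32% | 0.16% | 92.03% |
| 20% | 6% / 2.25% | 35.5 / 98 | 72.48 | 0.71% | 0.36% | 92.13% |
| 20% | 7.5% / 1.875% | 28 / 118 | 71.83 | 1.61% | 0.81% | 92.35% |
| 10% | 15% / 1.67% | 13 / 133 | 69.16 | 5.26% | 2.67% | 93.24% |

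For example, in the second row 1/(0.2/35.5 + 0.8/98) = 72.48, and 1 − 72.48/73 = 0.71%. The variance ratio is 1.0072, equivalent to about 34,000 × 0.0072 ≈ 244 women. A simulation of 400 trials (32,980 women, 8 sites, robust Poisson) gave an SE ratio of 0.997 for the second row and 0.976 for the last, with the relative risk essentially unchanged.

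**Neonatal outcome, gestational age.** The documents give no preterm share and no risk ratio, so both are assumptions here. With an 8% composite, v(0.08) = 26.125.

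- 5% preterm at 2 times the risk: variance cut 0.38%.
- 10% preterm at 3 times the risk (20% against 6.67%): 1/(0.1/9.25 + 0.9/31.75) = 25.54, a cut of 2.25%.
- 15% preterm at 5 times the risk: variance cut 7.08%.

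Over the same assumptions a 14% composite gives about 0.8-15%. High-risk status alone, at an assumed doubling of neonatal risk and a 10-20% share, gives 0.65-0.94%. Power for a 20% reduction from 8% is already 99.99% and does not move.

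**The case against.** The strongest reply is that nothing here is wrong. Treatment plus site is pre-specified, is the same in protocol and SAP, and matches the only stratification factor. The gain at the plan's own maternal figures is under 0.4% in the standard error, and SAP 11 already calls the trial extremely well powered for the neonatal outcome. SAP 7.2 promises known predictors in secondary analyses, and SAP 9.4 fits a treatment by risk-status interaction. All of that stands, and it is why this is an optional improvement.

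Two parts of the reply do not fully answer the point. The secondary covariates are not named. The interaction model in SAP 9.4 asks whether the effect differs by risk status and excludes women who become high-risk after randomization, so it does not provide an adjusted estimate in the full ITT population.

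Two practical cautions also stand. If risk status or prematurity varies by site, the site terms already capture part of the gain. And protocol Appendix 3 schedules labor and delivery information for collection after delivery. The high-risk covariate must therefore be built from labor-onset and membrane-rupture times relative to randomization; those data are collected under masking.

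A reader might also infer that the imputation and analysis models are misaligned because high-risk status appears only in the former. The documents do not support that: an imputation model may carry predictors that the analysis model lacks.

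**Conclusion.** The primary analysis is valid, and the planned sample size gives maternal power of about 92% against the stated 90%. Reading the omission as a source of bias or as a shortfall in power would go beyond the documents. What remains is a small, avoidable loss of precision and a gap in pre-specification: neither high-risk status nor gestational age is assured as an adjustment covariate.

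For the maternal outcome the loss is 0.3-0.7% of variance at the 6% and 3% planning risks (0.1-0.2 points of power). It is 1.6-5.3% (0.4-1.3 points) if high-risk women carry half of the events. That second figure comes from a statement about infections in general, with the high-risk share depending on the criteria used, so it is less secure for death or sepsis. For the neonatal outcome, 0.4-7% rests entirely on the assumed preterm share and risk ratio. The only support in the documents concerns mortality, whereas non-fatal sepsis is about 4-10 points of the assumed 8-14% composite. The benefit there is a narrower interval only.

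**What to change.** Before unmasking, amend SAP 7.2 and 9.3 as follows.

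- Add high-risk status at randomization (yes/no) to both primary models, and gestational age (<37 or ≥37 weeks by best estimate) to the neonatal model.
- Fit a log-link model with robust variance, keeping the allowance for multiples. The existing convergence fallback in SAP 9.3 covers only the correlation structure.
- Put the same covariates in the matching imputation model. High-risk status is already there; gestational age must be added for infants, otherwise the neonatal analysis model would contain a covariate that its imputation model lacks.
- State one simple rule for missing covariate values.
- Keep the site-only model as a sensitivity analysis, and record the change from protocol 3.1.1 in SAP section 12, which is now empty.

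Staff masked to interim results should make the decision, in line with SAP 7.6. If the trial has been unmasked, report the adjusted model only as a named supportive analysis. The cost is minor SAP wording and the missing-covariate rule; no extra participants or data collection are needed.

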9.2 Definition of Analysis Variables

As clinical assessments/diagnoses and associated care may lag behind actual occurrence, any infection events, antibiotic use, or other medical care (e.g. admissions, unscheduled visits) documented prior to the end of the relevant visit window will be counted. Mortality outcomes will be defined in accordance with traditional Global Network algorithms only including events occurring specifically within the window detailed in the outcome definition below.

Additionally, most infections are expected to occur within the first week following delivery. Therefore, mothers or infants that are lost to follow-up after completion of a Day 7 visit with no signs or symptoms of infection prior to becoming lost to follow-up will be considered to meet criteria to have the primary outcome ascertained as no infection or death. Mothers or infants lost to follow-up prior to completion of a Day 7 visit with no signs or symptoms of infection will be considered to have missing outcomes.

Variable	Type	Definition
Primary Outcomes		
Maternal death and/or sepsis through 42 days Primary Composite Outcome	Binary	
The event will be defined as “Yes” if either component of this composite outcome is “Yes” and “No” if both components of the composite are “No.” Any subsequent missing values will be included in the primary analyses using multiple imputation procedures.
 
Analysis population(s): ITT (all-comer and high risk; with and without imputation), Per-Protocol

Intrapartum/neonatal death and/or sepsis through 28 days Primary Composite Outcome	Binary	
The event will be defined as “Yes” if either component of this composite outcome is “Yes” and “No” if both components of the composite are “No.” Any subsequent missing values will be included in the primary analyses using multiple imputation procedures.
 
Analysis population(s): ITT (all-comer and high risk; with and without imputation), Per-Protocol

Secondary Outcomes		
Maternal death through 42 days Component	Binary	
The event will be defined as “Yes” if the woman dies prior to 42 days after delivery and “No” otherwise. This outcome measure will be obtained from form MN06 (i.e. presence of a form indicating a death has occurred). If the 42-day outcome is missing and the woman was alive at the last known follow-up, this outcome will be treated as missing when analyzed alone.
 
Analysis population(s): ITT (all-comer and high risk), As Treated

Variable	Type	Definition

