Maternal death due to sepsis through 42 days	Binary	
The event will be defined as "Yes" if the woman dies prior to 42 days after delivery with the cause of death determined to be sepsis and "No" otherwise (i.e. if the woman is alive or died due to other causes). This outcome measure will be obtained from form MN06 (i.e. as defined by the MNH algorithm). If the 42-day outcome is missing and the woman was alive at the last known follow-up, this outcome will be treated as missing when analyzed alone.
 
Analysis population(s): ITT (all-comer and high risk)

Variable	Type	Definition
Maternal sepsis through 42 days Component	Binary	
The event will be defined as "Yes" if the woman is diagnosed with sepsis prior to 42 days after delivery and "No" otherwise.
 
The details of defining this outcome are in the adjudication plan. In brief, where possible the outcome will be defined programmatically per the algorithm defined in the adjudication plan with cases that are unable to be programmatically determined route to adjudication. For the adjudicated outcomes, the value will be determined based on the reported final outcome reported by the site via form AZ13 (and confirmed via central adjudication). If the final outcome is "Insufficient data to make a determination," the outcome will be treated as missing. For sepsis confirmed by algorithm, the date of sepsis will be the visit date when the first confirmation criterion is met. For sepsis confirmed by adjudication the diagnosis date will be the diagnosis date recorded on the maternal adjudication form (AZ13A). If the adjudication diagnosis date is before delivery, then it is set to delivery date. If the adjudication diagnosis date is more than 3 days after the last unplanned care date with adjudication triggers, then it is set to the maximum of delivery date and unplanned care visit with adjudication triggers presentation and discharge dates. If the algorithm date is 1, 2 or 3 days before delivery and is equal to the first unplanned care date then the diagnosis date is set to delivery date. Analysis population(s): ITT (all-comer and high risk)

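### Suspected infections that cannot be adjudicated are imputed with the same model, and so at the same risk, as symptom-free early losses, although the trial records which participants were suspected cases

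*Combined protocol and SAP*

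**What the plan says.** Two kinds of missing primary outcome reach the same imputation.

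- **Symptom-free early losses.** SAP section 9.2 sets their outcome to missing, in a rule that begins "Mothers or infants lost to follow-up prior to completion of a Day 7 visit with no signs or symptoms of infection will be considered". Those "lost to follow-up after completion of a Day 7 visit with no signs or symptoms of infection" are instead counted as having no event and are not imputed.
- **Unresolved suspected infections.** In the section 9.2 rows for maternal and neonatal sepsis, when adjudication ends with insufficient data, "the outcome will be treated as missing". Section 7.3 names a main cause: "lack of record availability of unscheduled clinic visit, hospitalizations and readmissions required to diagnose infections".

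Section 7.3 sends both kinds to one procedure in the primary ITT analysis: "missing responses due to loss to follow-up and cases of suspected infection that cannot be adjudicated will be included via multiple imputation procedures". Section 9.3 specifies the model, fitted separately for mothers and infants, as "logistic regression imputation using site and high-risk status prior to randomization as covariates". It lists no sign, symptom, adjudication trigger, antibiotic or culture variable.

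Section 7.3 concedes that missing records may violate missing at random. It relies on the proportion being small and on imputation being robust. The planned sensitivity analyses use available data, count all missing outcomes as events, and count none as events. Further analyses follow only if more than 4% of data are missing.

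**The concern.** Imputation under missing at random is only as credible as the variables it conditions on. A woman routed to adjudication because of fever, whose readmission record cannot be found, differs in prognosis from a woman who left early with no sign of infection. The trial knows which is which: SAP section 4.4 describes an algorithm that routes cases for review, and the date rules in section 9.2 refer to forms carrying adjudication triggers. It will also know what share of triggered cases was confirmed. The imputation model uses neither fact. Robustness to non-ignorable missingness is not a general property of multiple imputation, and it is no reason to leave out an observed predictor.

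At stake is the sepsis count in the primary analysis of both outcomes. If the number of unresolved suspected cases does not follow the event rate in each arm, the relative risk is affected too.

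**Working it through.** **Inputs from the documents.** 34,000 women, 1:1, so 17,000 per arm. Maternal placebo risk 3% with a 20% reduction, giving 2.4%. Neonatal risk at the lower planning value of 8%, with a 20% reduction, giving 6.4%. Two-sided alpha 0.05.

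**Inputs assumed.** The SAP gives no rate for unresolved suspected cases and says only that it should be low. I take u = 0.2% to 1% of women, with a true sepsis share c = 30% to 50%.

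**The plan's own figure.** With the pooled-variance formula,

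n = [1.960 × √(2 × 0.027 × 0.973) + 1.282 × √(0.03 × 0.97 + 0.024 × 0.976)]² / 0.006² = 15,334 per arm.

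This matches Table 1. Allowing 3% loss, 15,334 / 0.97 = 15,809, below 17,000. The design figures are not in dispute.

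**Imputed risk.** Arm is not among the listed covariates, so the average is over both arms: (3.0% + 2.4%) / 2 = 2.7% for mothers and (8% + 6.4%) / 2 = 7.2% for infants. These are also the break-even values: events are understated only if c is higher.

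**Maternal events lost.** Expected events are 17,000 × 0.03 + 17,000 × 0.024 = 510 + 408 = 918. Events lost = 34,000 × u × (c − 0.027).

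| u | Women unresolved | Imputed events | True events, c = 30% to 50% | Lost | Share of 918 |
|---|---|---|---|---|---|
| 0.2% | 68 | 1.8 | 20 to 34 | 19 to 32 | 2.0% to 3.5% |
| 0.5% | 170 | 4.6 | 51 to 85 | 46 to 80 | 5.1% to 8.8% |
| 1.0% | 340 | 9.2 | 102 to 170 | 93 to 161 | 10.1% to 17.5% |

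**Neonatal events lost.** Taking about 34,000 infants, expected events are 34,000 × 0.072 = 2,448. At u = 0.5%, 170 × (0.30 − 0.072) = 39 to 170 × (0.50 − 0.072) = 73 events are lost, or 1.6% to 3.0%. The relative loss is smaller than for mothers.

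**Relative risk (maternal).** RR = [408 − 17,000 × u_A × (c − 0.027)] / [510 − 17,000 × u_P × (c − 0.027)], where A is azithromycin and P is placebo.

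| u_P vs u_A | RR, c = 30% | RR, c = 50% | Power |
|---|---|---|---|
| 1.0% vs 0.8% (proportional to events) | 0.80 | 0.80 | 0.90 to 0.88 |
| 0.6% vs 0.4% | 0.81 | 0.81 | 0.89 to 0.85 |
| 0.5% vs 0.5% | 0.79 | 0.78 | not computed |
| 1.0% vs 0.5% | 0.83 | 0.86 | 0.78 to 0.60 |

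Power with complete data is 0.927 at 17,000 per arm. If 5% of true maternal sepsis were non-adjudicable in both arms, it would be about 0.915.

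**Planned sensitivity analyses.** At 2% missing, counting every missing outcome as an event gives (0.024 × 0.98 + 0.02) / (0.03 × 0.98 + 0.02) = 0.0435 / 0.0494 = 0.88. This adds 34,000 × 0.02 = 680 events, symptom-free losses included. The available-case analysis drops the suspected cases, and the no-event analysis sets them to zero. SAP section 7.3 expects loss of 2% or less, with 1.1% in the pilot, so the 4% threshold may well not be reached.

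**The case against.** The strongest reply is that the problem may be very small. SAP section 7.3 expects few non-adjudicable cases and commits to estimating their share from pilot data before unmasking. If 918 events came from suspected cases confirmed 30% to 50% of the time, there would be about 1,836 to 3,060 suspected cases. Then 170 unresolved is 6% to 9% of them and 340 is 11% to 19%; the latter fits poorly with a low rate. This stands, and it makes the upper end of the range less likely.

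The all-event and no-event analyses also bracket the event count in each arm. That stands too, but they treat all missing outcomes alike.

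For infants, the definition in SAP section 3.1 joins the clinical signs by and/or, so one recorded sign may be enough, and unresolved cases may be fewer. In either group a known death makes the composite positive whatever the sepsis adjudication. How often a participant who leaves with signs ends as insufficient data depends on a separate adjudication plan that is not among the documents.

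Two stronger readings are tempting:

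- **Suspected cases are filled in at the near-zero risk of a symptom-free participant.** The documents do not support this. The model draws from the average risk at that site and risk status, which includes confirmed sepsis.
- **The treatment effect is materially biased.** The shift to 0.83 to 0.86 needs twice as many unresolved cases on placebo. Treatment and adjudication are masked, and no mechanism for such an imbalance is documented. With equal proportions in both arms the shift is slightly in the other direction.

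**Conclusion.** The point holds as a weakness in the primary imputation model: it treats unresolved suspected infections and symptom-free early losses alike and ignores an observed predictor of sepsis. Understatement follows if more than about 2.7% of unresolved suspected mothers, or 7.2% of such infants, are truly septic. That is very plausible, but the documents give no figure for it.

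On the assumed ranges the maternal loss is about 2% to 18% of events. The main consequence is on absolute risks and, to a lesser degree, power. The effect on the relative risk is negligible when unresolved cases scale with events and about 0.01 under a moderate imbalance. If unresolved cases are as rare as the SAP expects, the whole effect is small. The change is still worth making before unmasking, because it concerns both primary outcomes and uses data already held.

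**What to change.** In SAP section 9.3, replace the single imputation by two parts, for mothers and infants separately:

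1. Impute unresolved suspected cases from participants who met an adjudication trigger and whose outcome was determined, with site and high-risk status as covariates and sites pooled where sparse.
2. Keep imputing symptom-free losses before Day 7 from the overall site and risk-status model.

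A single yes/no trigger variable would be simpler but should be avoided. It would code early losses as having no trigger, although their later status is unobserved, and give them the very low risk of fully followed, never-triggered participants. Sepsis being almost absent without a trigger could also cause quasi-separation in the logistic model.

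Add a sensitivity analysis that counts only the unresolved suspected cases as events, and report their number by arm. Part 1 still assumes that resolved and unresolved triggered cases are alike within site and risk status; this analysis tests the high-risk side of that assumption.

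The cost is a short SAP change, a two-part imputation and some pooling across sparse sites. The information that routes cases to adjudication already exists, and SAP sections 5 and 7.6 already provide for an addendum after masked review.
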